3. PATIENT SELECTION CRITERIA

Patients under surveillance for small AAA are identified through local registers at respective site. Those with the most recently examined AAA are screened for eligibility. All patients scheduled for enrolment visit are accounted for.

3.1 Inclusion criteria

For inclusion in the study patients should fulfil the following criteria:

- 1. Provision of written informed consent.
- 2. Male and female patients.
- 3. Age 50-80 years.
- 4. Documented AAA Ø 30-49 mm for men and 30-44 mm for women.
- 5. Fasting p-glucose <7.0 mmol/L (WHO 1999). Fasting is defined as no caloric intake for >8 h.

3.2 Exclusion criteria

Patients should not enter the study if any of the following exclusion criteria are fulfilled:

- 1. Short expected survival.
- 2. History of current or previous diabetes mellitus.
- 3. Current or previous use of metformin.
- 4. Not expected to tolerate metformin.
- 5. Contraindications to metformin treatment according to SmPC:
 - a Renal failure with glomerular filtration rate (GFR) <45ml/min according to the revised Lund-Malmö formula.
 - b Hypersensitivity to metformin or any of the excipients included in the tablet.
 - c Acute metabolic acidosis.
 - d Diabetic pre-coma.
 - e Acute conditions with the potential to alter renal function such as; dehydration, severe infection or shock

- f Acute or chronic disease which may cause tissue hypoxia such as; decompensated heart failure, respiratory failure, recent myocardial infarction or shock
- g Hepatic insufficiency, acute alcohol intoxication, alcoholism
- 6. Known or suspected connective tissue disorder (Marfans syndrome, etc), infected or inflammatory aneurysm, aneurysm development after aortic dissection or previous surgery of the infrarenal aorta.
- 7. Enrolment in either another investigational drug or medical device study or another investigational study of an approved drug or medical device within 30 days prior to enrolment of the current study.
- 8. If, in the opinion of the investigator, it is not in the patient's medical interest to participate in the study or the patient is unlikely to be able to comply with the study protocol.
- 9. Pregnancy. Women of childbearing potential are only included after a confirmed menstrual period and a negative highly sensitive urine or serum pregnancy test as well as willingness to comply with highly effective anti-contraception throughout the study period, see 5.3.

4. STUDY CONDUCT

4.1 Treatment

The treatment allocation in this study will consist of;

- Study Arm 1; Metformin tablets taken orally with target dose of 2g daily
- Study Arm 2; Standard care as described in current AAA guidelines (Wanhainen 2019)

Standard care includes help with smoking cessation if applicable; encouragement of physical activity and a healthy diet; blood pressure control; statin and anti-platelet therapy treatment if the patient have clinical manifestations of atherosclerotic disease. Local guidelines dictate which classes of drugs are recommended and who is responsible for treatment and follow up. The study participants allocated to metformin receive standard care plus metformin treatment.

Patients will be encouraged to take metformin every day at similar times, preferably with a meal to minimize side effects.

Metformin is titrated stepwise to avoid gastrointestinal side effects. Starting dose is one tablet of metformin 500mg day 1-14, two tablets day 15-28, three tablets day 29-42 and four tablets daily from day 43 till the remainder of the study. If a patient misses one dose he/she is

encouraged to take one extra tablet with the following dose. No more than one dose should be compensated for if missed.

If a patient has severe side effects in the run-in phase, titration to target dose will be slowed. If a patient has severe side effects at the target dose, the target dose will be reduced to a level at which the side effects are tolerable and stay at this level for the remainder of the study. Target dose and compliance to this dose is recorded at each contact.

Table 2. Identity of investigational product(s)

Investigational product	Dosage form and strength	Study arm and time point
Metformin	Tablet 500mg, 1 daily	Study arm 1, Day 0-14
Metformin	Tablet 500mg, 2 daily	Study arm 1, Day 15-28
Metformin	Tablet 500mg, 3 daily	Study arm 1, Day 29-42
Metformin	Tablet 500mg, 4 daily	Study arm 1, Day 43-completion

Target dose of metformin 2g is chosen to reflect doses given in observational studies. It is predicted to be a sufficient dose to translate to a meaningful biologic effect whilst still safe and with acceptable side effects. The option to reduce the dose is expected to reduce drop-out rate. Once the final target dose is reached a different metformin tablet strength may be used for convenience, i e 1g rather than 500mg tablets.

4.1.1 Labelling

The study medication will be prescribed by the investigator and retrieved by the patient at the pharmacy. The prescription note will state that the drug is used for study purpose. The patients are being reimbursed for their study drug costs.

4.1.2 Procedures for randomisation

On signing the Informed Consent the patients will be enrolled (enrolment = the process of allocating a unique identifier to a patient on entry into a clinical study, after obtaining written Informed Consent) and identified with a unique enrolment code (E-code) of 4 digits where the first digit is the site number and the three following the patient number. Uppsala=1, Malmö=2, Gävle=3, Västerås=4, Karlstad=5, Falun=6, and Umeå=7.

Enrolment will take place before treatment randomisation (randomisation = the assignment of patients to treatment in a clinical study according to a randomisation schedule generated by a random process) to assure allocation concealment. A randomisation list will be generated using a computerized procedure, by sorting 275 treatment allocations in each arm in random order using Excel (Microsoft, WA, USA). A total of 550 treatment allocations will be generated to accommodate possible erroneous entries to the database. Patients will be randomised strictly sequentially as they are eligible for randomisation. Simple randomization will be used without stratification given the large number of subjects.

The patients will be randomized on a 1:1 schedule to; metformin tablets in incremental doses to 2g daily *or* standard care.

If a patient discontinues from the study, the patient number will not be reused, and the patient will not be allowed to re-enter the study.

4.1.3 Compliance

The patient is asked to note missed doses of medicine for any reason. The patient brings used bottles of metformin and receipts from the pharmacy at the study visit and remaining doses are counted to calculate compliance. Three consecutive days or more of missed medication are noted separately.

4.1.4 Concomitant treatment(s)

Medication, which is considered necessary for the patient's safety and well-being, may be given at the discretion of the investigator(s).

All medication is allowed, except for antidiabetic agents. If the need for antidiabetic medication should arise, the patient is discontinued from the study.

The study protocol includes patient history and measures of cardiovascular function such as blood pressure, heart rate and cardiac and respiratory auscultation. If un- or undertreated diseases or risk factors are discovered, treatment will be initiated as appropriate or the patient is referred to relevant care. Active smokers are encouraged to smoking cessation.

It is likely that CT imaging will generate accidental findings in some patients. These findings will be dealt with according to clinical praxis at respective site. It is the responsibility of the investigator at respective site to make sure relevant care is provided for patients with accidental findings on imaging, laboratory tests or physical examination.

Concomitant medications will be recorded in the medication list in the eCRF.

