2. STUDY PLAN AND PROCEDURES

2.1 Study design

The MAAAGI-trial is a population-based multi-center, prospective, parallel group, randomized, open label trial with blinded outcome assessment to assess if metformin up to 2g daily over a five-year period will reduce AAA growth in patients who do not have diabetes.

Patients will be recruited from a cohort of patients with diagnosed AAA at the following seven Swedish sites; 1) Uppsala University hospital, Uppsala, 2), Skåne University hospital, Malmö, 3) Gävle county hospital, Gävle, 4) Västerås county hospital, Västerås. 5) Karlstad county hospital, Karlstad 6) Falun county hospital, Falun, and 7) Umeå University Hospital, Umeå.

The patients should have a maximum aortic diameter of 30-49mm for men and 30-44mm for women, not have diabetes and be expected to tolerate metformin.

A total of 500 patients with AAA will be included in the study, 250 in each study arm. Patients will be randomised to metformin or standard care in a 1:1 ratio.

The patients are scheduled for one enrolment visit, eight study visits and ten phone contacts for those randomized to metformin (three to support titration of study drug) and seven phone contacts for those randomized to standard care. The study visits will take place at the vascular laboratory at the respective surgical departments for clinical examination and blood sampling and at the CT units at the radiology departments where CT-imaging will be performed.

After a run in phase to support titration of metformin, visits and phone contacts are scheduled to alternate every three months until 24 months and twice yearly thereafter. CT imaging and AAA US will be performed at baseline, 24 months and end of study, as well as if necessary according to clinical routine. Study drug will start at baseline and continue through completion.

End of study is defined as 1) study completion at 60 months, or 2) discontinuation from study before that for any reason, for example due to AAA repair or patients will.

When all patients have completed the 24-month follow-up (including imaging) an interim analysis will be performed to assess for efficacy and safety; if there is no trend towards a positive effect or signs of a harmful effect of metformin, the study will be stopped at this phase.

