4.2 Withdrawal from study

Patients may be discontinued from the study at any time, at the discretion of the investigator.

Patients are free to discontinue their participation in the study at any time for any reason.

Patients who discontinue from the study should always be asked about the reason(s) for the discontinuation (and informed about their right not to disclose their reason for doing so) and the presence of any adverse events (AEs). If possible, they should always be seen and assessed by an investigator and asked to perform completion outcome measures, including CT, US and QoL questionnaires. A pre-operative CT may be used for follow up should indication to operate the aorta arise. Adverse events should be followed up.

Study treatment should be stopped in the following cases: development of diabetes, persistent renal failure with GFR<45ml/min, severely deteriorating health, aortic surgery or onset of exclusion criteria.

If the study medication is stopped, patients will be asked to remain in the study and follow the other procedures according to the protocol. All randomised patients remain in the group they were originally allocated to for the purpose of intention-to-treat (ITT) analyses.

Patients who discontinue the study will not be replaced.

Sponsor has to be informed if a patient is withdrawn by any reason before study end. The "End of study" form must be filled out by the investigator and the reason should be stated.

The study number will not be reused if a patient is withdrawn.

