8.1 Analysis set

All patients for whom a signed informed consent was obtained and an eCRF was started will be accounted for.

The Safety Analysis Set will include all patients who received at least one dose of study drug.

An intention-to-treat (ITT) analysis will include all randomised patients who received at least one dose of study drug and for whom at least one post dose observation for an efficacy endpoint is recorded.

The per-protocol analysis (PPA) consists of patients who sufficiently complied with the protocol. Inclusion in the PPA will require at least the following:

- An at least 80% compliance with the intended use will be accepted as per protocol.
- No major protocol deviations.

• Measure of primary efficacy endpoint at 60 months after baseline, and at 24 months for the interim analysis.

All efficacy analyses will be performed as both ITT and PPA. The ITT analyses is to be considered as main and the PPA as supportive.

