8.2 Outcome variables

8.2.1 Primary variable

Efficacy in this study will be assessed by difference of AAA diameter determined by CT after 24 and 60 months vs at baseline, expressed as mm/year. The primary outcome is effect on AAA growth rate following 60 months metformin treatment vs standard care.

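### Section 4.1.4 removes from follow-up patients who need antidiabetic drugs, against the stay-in-study rule of 4.2, creating avoidable missing outcomes that may differ by arm

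*Combined protocol and SAP*

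**What the plan says.** Two rules in the combined protocol and SAP deal with diabetes that arises during the trial.

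- Section 4.1.4 allows all concomitant drugs except antidiabetic agents, and then states: "If the need for antidiabetic medication should arise, the patient is discontinued from the study". It does not distinguish between arms.
- Section 4.2 states: "Study treatment should be stopped in the following cases: development of diabetes", among other triggers, and continues: "If the study medication is stopped, patients will be asked to remain in the study and follow the other procedures according to the protocol". It also keeps every randomised patient in the allocated group for intention-to-treat analysis.

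Patients who leave are, where possible, "asked to perform completion outcome measures, including CT, US and QoL questionnaires" (4.2). Section 2.1 says that "CT imaging and AAA US will be performed at baseline, 24 months and end of study", and its definition of end of study includes "discontinuation from study before that for any reason". An exit CT may therefore exist for a removed patient.

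On analysis, 8.1 admits to the ITT set patients "for whom at least one post dose observation for an efficacy endpoint is recorded". The primary variable in 8.2.1 is the diameter difference "determined by CT after 24 and 60 months vs at baseline, expressed as mm/year". Section 8.3 then restricts the primary analysis to patients with a value measured at the visit in question and leaves the others to imputation in sensitivity analyses. Table 1 gives the 60-month visit a window of 4 weeks either side. Section 5.1.2 provides for analysing an early CT in one case only: the preoperative scan of a patient who leaves for aortic surgery.

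**The concern.** A patient whose diabetes needs drug treatment meets both rules. One ends follow-up and the other continues it. No text says which prevails. A site could keep a metformin patient under 4.2 and remove a comparable control under 4.1.4, because a control has no study medication to stop and the stay-in-study sentence does not clearly apply. The trial is open-label.

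Removal follows an event after randomisation that treatment can influence: section 1.1 says metformin acts mainly by lowering blood glucose. If fewer metformin patients come to need antidiabetic drugs, fewer of them are removed. If the removed patients also grow at a different rate from the rest, the analysed arms are no longer the randomised arms. At stake is bias in the primary growth comparison at 60 months, and in the 24-month interim analysis for those who leave earlier.

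**Working it through.** **1. The two rules side by side.** Diabetes managed without drugs falls under 4.2 alone: stop study drug and stay. Drug-treated diabetes falls under both. If 4.1.4 is read as the specific rule that overrides the general one, the text is coherent, but drug-treated patients in both arms are removed.

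**2. What happens to the outcome.** Belonging to the 8.1 ITT set does not put a patient in the 60-month analysis, because 8.3 also requires a value at that visit. With the 4-week window, a CT at month 30, for example, is not a 60-month value. The end-of-study definition, the mm/year scale and the preoperative-CT rule blur this somewhat, but the plain reading is that an early exit CT is not used.

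**3. The plan's own sample size (8.4).** Inputs: growth 3 mm/year, SD 2.17, 30% reduction (0.3 × 3 = 0.9 mm/year), two-sided α 0.05, power 80%.

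n per arm = 2 × (1.96 + 0.842)² × 2.17² / 0.9² ≈ 91.3, rounded up to 92; total 184. The stated figure reproduces.

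With 250 per arm and 30% dropout, 250 × 0.7 = 175 per arm remain. Power for 0.9 mm/year is 94.1% with the SD 10% larger and 92.1% with it 15% larger. At 40% dropout (150 per arm) it is still 90.4% and 87.8%.

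**4. Standard error.** SD = 2.17 × 1.10 = 2.387; SE = 2.387 × √(2/175) = 0.255 mm/year.

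**5. Bias from removal.** The documents give no diabetes incidence, and scheduled fasting glucose is stated only at enrolment (5.1.1), so everything here is assumed. Let a fraction p of an arm exit, growing d mm/year slower than that arm's full mean, with no exit CT used. The analysed mean then rises by p × d / (1 − p). Bias = control shift − metformin shift; positive favours metformin. Assumed ranges: control p 5–12%, metformin p 3–8%, d 0.5–1.5, the same d in both arms.

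| Case | Control shift | Metformin shift | Bias (mm/year) |
|---|---|---|---|
| Midpoint: 8.5%, 5.5%, d = 1.0 | 0.085/0.915 = 0.093 | 0.055/0.945 = 0.058 | +0.035 |
| Lowest corner: 5%, 8%, d = 1.5 | 0.079 | 0.130 | −0.051 |
| Highest corner: 12%, 3%, d = 1.5 | 0.205 | 0.046 | +0.158 |

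Midpoint: 0.035/0.9 = 3.9% of the planned effect; 0.035/0.255 = 0.14 SE; two-sided type I error about 5.2%.

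Highest corner: 0.158/0.9 = 17.6%; 0.62 SE; type I error about 9.5%.

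With lower assumed rates (control 1–3%, metformin 0.5–2%) the range is −0.016 to +0.039 mm/year and type I error is at most 5.3%. The bias is zero if exits grow like the rest of their arm. The signs reverse if exits grow faster.

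**6. Cost of keeping patients.** Suppose 5–12% of controls start metformin for half of follow-up and it has the full effect (assumed). Dilution = 0.05 × 0.5 × 0.9 = 0.0225 to 0.12 × 0.5 × 0.9 = 0.054 mm/year. At 8.5% it is 0.038.

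**The case against.** The best defence is that 4.1.4 is simply the specific rule and 4.2 the general one. It then applies equally to both arms and limits contamination, since metformin is first-line treatment for type II diabetes (1.1). The plan also asks leavers for completion assessments, records the reason for leaving, expects substantial missing data, and plans several imputation analyses. These exits would be part of the 30% dropout already allowed for. At mid-range values, the dilution caused by keeping patients (0.038 mm/year) is about as large as the bias removed (0.035 mm/year).

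Much of this stands. The rules conflict only where they overlap, and informative dropout was not overlooked. But the hierarchy reading still ends follow-up in both arms after an event that treatment can affect. The imputations are sensitivity analyses and cannot recover outcomes the protocol chose not to collect. Dilution has a known, conservative direction, whereas the missingness does not. Contamination is no reason to stop collecting data.

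A reader might infer that the plan is silent on an exit CT at 60 months. It is not: 8.3 with the visit window points to exclusion. What is missing is an express statement for non-surgical exits.

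**Conclusion.** The point holds as an avoidable source of missing primary outcomes, possibly unequal between arms, with a cheap remedy. On mid-range assumptions the bias is about 0.04 mm/year, some 4% of the planned effect. That rests on assumed exit rates, an assumed growth difference equal in both arms, and no use of exit CTs.

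Two stronger readings are not supported. A reader might infer that the trial is biased in favour of metformin with type I error near 10%. That figure belongs to one corner of an assumed grid: a four-fold exit ratio and exits growing 1.5 mm/year slower, half the planning mean of 3. Nor do the documents fix the direction. Section 1.1 says aneurysms expand more slowly in people with diabetes, but it also reports a cohort in which slower growth was seen only in those prescribed metformin. A reader might also infer a loss of power; the figures of 92–94% at the planned dropout rule that out as the concern.

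**What to change.** Amend 4.1.4 to read the same way for both arms. A patient who needs antidiabetic medication stops study drug if on it, receives the treatment needed, stays in follow-up with the scheduled 24- and 60-month CT, ultrasound and quality-of-life assessments, and is analysed as randomised. The start of any antidiabetic drug is recorded. This extends the principle already in 4.2.

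An analysis leaving out CTs taken after the drug start may be added, but as supportive only and labelled as open to the same selection.

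As a minor clarification, 8.3 should confirm that a non-surgical exit CT outside the 60-month window is not a 60-month value in the primary analysis but may inform the imputation.

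The cost is a few sentences in an amendment and scans already scheduled. The downside is the dilution shown above, an assumed 0.02 to 0.05 mm/year towards no effect.

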4.2 Withdrawal from study

Patients may be discontinued from the study at any time, at the discretion of the investigator.

Patients are free to discontinue their participation in the study at any time for any reason.

Patients who discontinue from the study should always be asked about the reason(s) for the discontinuation (and informed about their right not to disclose their reason for doing so) and the presence of any adverse events (AEs). If possible, they should always be seen and assessed by an investigator and asked to perform completion outcome measures, including CT, US and QoL questionnaires. A pre-operative CT may be used for follow up should indication to operate the aorta arise. Adverse events should be followed up.

Study treatment should be stopped in the following cases: development of diabetes, persistent renal failure with GFR<45ml/min, severely deteriorating health, aortic surgery or onset of exclusion criteria.

If the study medication is stopped, patients will be asked to remain in the study and follow the other procedures according to the protocol. All randomised patients remain in the group they were originally allocated to for the purpose of intention-to-treat (ITT) analyses.

Patients who discontinue the study will not be replaced.

Sponsor has to be informed if a patient is withdrawn by any reason before study end. The "End of study" form must be filled out by the investigator and the reason should be stated.

The study number will not be reused if a patient is withdrawn.

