5.2.9 Laboratory safety assessment

At enrolment and every 12 months P-Creatinine will be analysed. Metformin may induce vitamin B12 deficiency after prolonged treatment and S-B12 is therefore assessed at 24 months. The blood volume will not exceed 40 mL at each visit, including concurrent blood samples for scientific reasons. Extra blood panels will be drawn at the discretion of the

investigator if there is concern for primarily renal or hepatic impairment due to alterations in clinical status or medication. Elevated fP-Glucose or P-Creatinine discovered at inclusion visit or throughout the study will be dealt with according to clinical praxis. Typically by referral to the patients family doctor.

The analyses will be performed at the local hospital laboratories and follow the Swedish biobank law for collecting blood samples in a clinical study. Tubes will be labelled and handled according to local routines and will be discarded after analysis.

Blood samples will be taken for scientific reasons in Uppsala and Malmö. Samples are centrifuged, frozen and stored for subsequent analysis in accordance with the Swedish biobank law for collecting blood samples in a clinical study.

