6.3 Risks – Benefits

The uncertain knowledge state supporting the study-hypothesis emphasizes the importance of a risk assessment for each patient. A risk determination of potential risks in this study has been made. These risks together with the actions to minimize these risks are compiled below:

RISKS	ACTION
Suspected drug related adverse event, such as gastrointestinal events	If not tolerated, treatment with study drug should be reduced in dose or stopped, temporarily or permanent, and appropriate medical action should be initiated according to the nature and severity of the AE.
Patient require surgery or intravenous contrast media during study	Temporary discontinuation of the study drug according to clinical praxis for metformin. Typically 48 h after intravenous contrast media, in the perioperative phase and during fasting.
Patient develops suspect or manifest dehydration during study	If risk of dehydration for any reason the study drug is temporarily discontinued. This typically includes but is not limited to fever, serious infection, vomiting, diarrhoea and reduced fluid intake.
Patient develops suspect or manifest hypoxia during study	If risk of hypoxia for any reason the study drug is temporarily discontinued. This typically includes but is not limited to, sepsis, chock, myocardial infarction and decompensated heart failure.

Patient requiring continuous treatment with drugs that may temporarily affect renal function, such as NSAIDs	Study drug should be discontinued during treatment if there is evidence of renal impairment
Patient develops B12 deficiency secondary to metformin treatment BENEFITS	S-B12 levels are controlled every 24 months and replacement therapy is initiated if indicated

Other than obtaining an extensive medical evaluation and close monitoring of the AAA, no clear benefit was identified for the patients who participate in the study.

Table 2, possible risks and planned action

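### Section 4.2 stops metformin on onset of any exclusion criterion, which makes its condition of persistent low GFR redundant and conflicts with the temporary-withdrawal rules in 5.2.7 and 6.3

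*Combined protocol and SAP*

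**What the plan says.** Section 4.2 gives the stopping cases in one sentence. After the development of diabetes, it lists "persistent renal failure with GFR<45ml/min, severely deteriorating health, aortic surgery or onset of exclusion criteria".

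The closing item points back to section 3.2. Criterion 5a there reads "Renal failure with glomerular filtration rate (GFR) <45ml/min according to the revised Lund-Malmö formula", with no requirement that the low value persist. Criterion 5e reads "Acute conditions with the potential to alter renal function such as; dehydration, severe infection or shock". Criterion 5f adds acute or chronic causes of tissue hypoxia, including decompensated heart failure, recent myocardial infarction and shock. All three are listed as contraindications to metformin.

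Section 5.2.7 provides for temporary withdrawal in vomiting, diarrhoea, fever, poor fluid intake, dehydration and lactic acidosis. The drug carries on once the dehydration risk or temporary renal impairment has passed. The risk table in 6.3 likewise provides for temporary discontinuation when there is a risk of dehydration (serious infection is an example) or of hypoxia (sepsis, shock, myocardial infarction and decompensated heart failure are examples). A separate row, for patients who need continuous treatment with drugs such as NSAIDs, says "Study drug should be discontinued during treatment if there is evidence of renal impairment".

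On testing, section 5.2.9 says "At enrolment and every 12 months P-Creatinine will be analysed" and leaves additional panels to the investigator's judgement. On results, it says "Elevated fP-Glucose or P-Creatinine discovered at inclusion visit or throughout the study will be dealt with according to clinical praxis", typically by referral to the family doctor. It does not mention the study drug there.

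**The concern.** A site that receives a GFR below 45, or sees a patient with dehydration or an infarction, needs one answer about the study drug. The protocol offers several. Section 4.2 qualifies low GFR by persistence and then, in the same sentence, refers to a criterion without that qualifier. The same closing item turns acute states into reasons to stop, while two other sections treat them as reasons to pause.

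Seven sites make these decisions separately, and only the metformin arm has a drug to stop. Two things are at stake. One is exposure to metformin in a state that the protocol itself lists as a contraindication. The other is classification in the per-protocol analysis: section 8.1 requires at least 80% compliance and no major protocol deviations, and whether continuing or resuming the drug counts as a deviation depends on which section is taken to govern.

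**Working it through.** The check is mainly a comparison of text. The plan states no figure on this point that could be reproduced.

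**1. Persistence against the closing item of 4.2.** Take a first GFR below 45 in a patient who is otherwise well.
- Under the renal item of 4.2, the case is not yet met, because persistence has not been shown.
- Under the closing item of 4.2, read with 5a, the case can be met at once. The one qualification is that 5a speaks of renal failure with GFR below 45, and the protocol does not say whether a single estimate is enough.
- The items are alternatives joined by *or*, so meeting either is sufficient to stop. Any value that meets the persistent item also meets 5a. The persistent item therefore adds nothing.

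**2. Stopping against pausing.**

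| State | 4.2 through 3.2 | 5.2.7 | 6.3 |
|---|---|---|---|
| Dehydration | 5e: stop | Pause, then continue | Temporary discontinuation |
| Severe infection | 5e: stop | Pause if fever or dehydration is present | Temporary discontinuation |
| Shock | 5e, 5f: stop | Not named | Temporary discontinuation |
| Recent myocardial infarction, decompensated heart failure | 5f: stop | Not named | Temporary discontinuation |
| Temporary renal impairment with GFR below 45 | 5a: stop | Continue after resolution | Not covered, except with NSAID-type drugs |

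Section 4.2 has no provision for restarting, and it lists these states beside the development of diabetes and aortic surgery.

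**3. How persistence could be shown.** Neither a number of values nor an interval is given. Sections 5.1.1 and 5.2.9 schedule creatinine every 12 months. Table 1 allows 4 weeks either side of each visit.
- Nominal gap: 365.25 days.
- Window at both visits: 4 + 4 = 8 weeks = 56 days.
- Shortest gap: 365.25 − 56 = 309.25 days; 309.25 / 30.4375 = 10.2 months.
- Longest gap: 365.25 + 56 = 421.25 days; 421.25 / 30.4375 = 13.8 months.

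On scheduled tests alone, a second value comes about 10 to 14 months after the first. A first low value at the 48-month visit would have its next scheduled test at completion, when study treatment ends. Discretionary panels can shorten the gap to any length, but none is required. Section 5.2.9 ties them to concern arising from a change in clinical status or medication, and an isolated low annual value in a well patient is not plainly such a change.

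**4. Link from result to drug decision.** Section 5.2.9 sends a raised creatinine to ordinary clinical practice and does not refer to 4.2.

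**The case against.** The best defence is that the sections form a sensible scheme when read together: temporary impairment means pause (5.2.7, 6.3), persistent impairment means stop (4.2). That gives the word persistent a purpose and may well be what was intended. It does not rescue the text, because the closing item of 4.2 also covers the temporary states. In addition, the situations listed in 5.2.7 are mostly clinical, so an isolated low annual GFR is not expressly covered by it. One may add that 4.2 never says the stop is permanent. That is true, but a reader would have to supply the restart from another section.

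Several stronger readings are tempting, and the documents do not support them.
- *The protocol gives opposite orders on one GFR result.* It does not. The items in 4.2 are alternatives, and no section instructs a site to keep giving metformin at a GFR below 45. The persistence condition is redundant, not a contrary instruction.
- *Persistence cannot be shown for about a year.* This holds only for the scheduled tests, since 5.2.9 allows extra panels. The accurate statement is that no confirmatory test or interval is required.
- *Section 5.2.9 is a competing instruction.* Referral can accompany a stop. The weakness is the missing link to the drug decision.
- *The renal row of 6.3 is a general rule.* It covers only patients on drugs such as NSAIDs.
- *The between-arm GFR comparison is damaged.* This is not shown. Patients who stop the drug are asked to stay in the study and follow its other procedures, and Table 1 does not limit the yearly blood samples to the metformin arm.

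**Conclusion.** The point holds as a conflict between stated rules. The closing item of 4.2 makes the persistence condition redundant and, for the acute states in 5e and 5f, is at odds with the temporary withdrawal in 5.2.7 and 6.3. Persistence is undefined, and the only required tests are about 10 to 14 months apart. Depending on the section followed, a site can stop, pause or continue the drug on the same finding.

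The consequence is inconsistent exposure in a state listed as a contraindication, and possibly inconsistent per-protocol status. Under 4.2, patients who stop the drug keep their allocated ITT group and are asked to remain in follow-up, so this wording does not disturb either. The number of patients affected cannot be estimated, because the documents give no rate of GFR decline or of the acute conditions. The upper end of the testing interval assumes that no extra panel is drawn. The reading of 5a assumes that a GFR below 45 can be taken as renal failure in the sense of that criterion.

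**What to change.** Reconcile sections 3.2 (criteria 5a, 5e and 5f), 4.2, 5.2.7, 5.2.9 and 6.3, so that one consistent wording covers both low GFR and the acute exclusion conditions.
- In 4.2, make clear how the closing item relates to the GFR item and to temporary withdrawal under 5.2.7 and 6.3.
- If the word persistent is kept, state how it is established: which tests count and over what interval.
- In 5.2.9, add a cross-reference from a raised creatinine to the study-drug decision in 4.2, alongside the referral.

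Which clinical rule applies is for the sponsor to decide. The cost is a wording amendment across these five sections. Extra creatinine tests are already permitted by 5.2.9; making a repeat test mandatory, should the sponsor choose that, would add blood samples for the patients concerned. The sample size and the primary analysis do not change.
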